3.1 Outcome Measures

The primary outcome will be the resuscitation performance retention assessed using the post-teaching the final global rating scale score (1-7 performance score) for medical management and flow during each simulation as well as the following “time-to” metrics; glucose check, IV access, chemistry panel order, first-line anti-epileptic administration³⁰, second line anti-epileptic administration. This will be adjusted for baseline score.

The secondary outcome measures for knowledge retention assessment will be the post-teaching knowledge test score assessed on a 15 Question MCQ test administered at the final assessment adjusted for the baseline score.

Comfort/Confidence will be assessed using the change in Likert scale item after each simulation and debrief.

4 Study Population

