4.2 Expected Duration of Subject Participation

A participant will already be expected to attend a 60 min teaching session on status epilepticus. They will also be required to participate in two 10-25 min simulation sessions which will include a 10-minute simulation and 15 debrief for the first and only a 10-minute simulation the second time.

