The LS group will complete the 60-minute focused lecture immediately prior to their initial simulation. The SL group will complete the 60-minute focused lecture immediately after their initial simulation. The LS group will complete a pre-intervention knowledge test prior to the lecture and the SL group will complete a knowledge test prior to the initial simulation.

Both groups will complete the initial simulation in groups of 3-4 with one member acting as the leader and others acting as team members. The simulation will last for 10 minutes followed by a structure debrief using the +/-delta method lasting up to 20 minutes. The debrief will be completed by a pediatric emergency medicine specialist with experience in leading simulation debrief. The leader of the group will be recorded for later subgroup analysis.

Every individual will complete a second evaluatory simulation 3 months after the initial simulation to evaluate the primary outcome of resuscitation performance retention. Each participant will act as the simulation leader with two actors who will function as a highly trained nurse and second physician but will not provide advice. The simulation will be videotaped. The participants will also complete a knowledge test prior after the second simulation.

Simulation videos will be reviewed as per the above data collection method to determine outcome measures. The simulations will be completed in the BCCH simulation center with a trained pediatric simulation expert and simulation facilitator. A high-fidelity mannequin will be used. It can seize and has appreciable chest rise and breath sounds. The participants will be instructed to assume all medications requested are drawn up in a syringe to the dose desired in the medication tray to decrease variability in time to metrics from difficulty in drawing up medications.

6 Statistical Consideration

6.1 Sample Size Determination:

The one paper assessing knowledge and skill retention comparing SL and LS structured teaching found a 13.42% difference in skill performance on transesophageal echocardiography²⁴ with the following means and std; LS group 71.90 (18.59) and SL group 85.32(15.63). Using a sample size calculator estimates a sample size of 60 with an alpha of 0.05 and power of 0.8³¹.

6.2 Statistical Analysis:

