The recorded simulation sessions will be reviewed by two separate pediatric emergency medicine and simulation experts who will evaluate the participants on the simulation global rating scale, a validated assessment tool for simulation. Inter-rater reliability will be calculated via Pearson correlation and ICC statistics, and the final reported value will be the mean of both reviewers.

The recorded sessions will also be reviewed to the time to metrics by two reviewers with a masked co-investigator serving as the tie breaker in times of significant discordance. Time zero for the “time to” metrics will be when the facilitator finishes the scenario description.

The mean and 95% confidence interval of the metrics will be calculated for each group. Post randomization scores will be compared using a paired t-test, and with mixed effects linear models using pre-randomization score as a covariate. Time-to-event measures will be displayed with Kaplan Meier graphs and median time, and tested with the log-rank test, and secondarily using Cox proportional hazards models. Regression models may include adjustment for baseline variables imbalanced between arms or prognostic of outcome. Secondary Likert outcomes will be assessed with a proportional odds model. All results will be presented with appropriate 95% confidence intervals. Statistical analysis will be completed with statistician support using R statistical software.

Protocol Deviations:

All deviations will be reported to the REB in a timely manner.

7 Data Handling and Record Keeping:

7.1 Data Management Responsibilities:

The data will be stored on a secure redcap data-server. The server will be password protected and only the research team will have access to the data. Participant data will only be stored de-identified. The video recordings will be stored on an encrypted external hard drive kept in the PI's office locked office in a locked drawer. The original video data would be deleted from the simulation center.

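### The primary performance outcome is adjusted for a pre-randomization score that the schedule never collects

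*Combined protocol and SAP*

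**What the plan says.** Section 3.1 defines the primary outcome as the final GRS (1 to 7) plus five time-to metrics and adds: "This will be adjusted for baseline score". Section 6.2 compares post-randomization scores by a paired t-test and by "mixed effects linear models using pre-randomization score as a covariate". Times are tested by log-rank, with Cox models as secondary. For the knowledge outcome, section 3.1 specifies a 15-question test "administered at the final assessment adjusted for the baseline score".

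The schedule allows two simulations per participant. Section 4.2: "They will also be required to participate in two 10-25 min simulation sessions". Section 5.4 on order: "The LS group will complete the 60-minute focused lecture immediately prior to their initial simulation", whereas "The SL group will complete the 60-minute focused lecture immediately after their initial simulation". On format, the first session reads "Both groups will complete the initial simulation in groups of 3-4 with one member acting as the leader", and the final one "Each participant will act as the simulation leader with two actors". Section 5.4 also gives both arms a knowledge test before any teaching. Section 5.2 has raters give a GRS for every simulation, so an initial-simulation score will exist.

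**The concern.** The covariate named for the primary outcome does not exist under the name it is given. Someone will have to choose a substitute, possibly after the data are in, and the two candidates are not equivalent.

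The knowledge pre-test comes before teaching in both arms and is harmless as a covariate. The initial-simulation score is measured after allocation and can be changed by the very thing under test, the order of lecture and simulation. LS students reach that simulation fresh from a lecture whose objectives, by section 5.3, match the outcome measures. SL students reach it untaught and, by section 1.1, not told the topic. Adjusting for such a score could credit SL with an advantage that it does not have at three months, and SL is the arm that the hypothesis favours.

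The paired t-test is a separate error. Nothing pairs an LS student with an SL student. If the pairing is read as within student, the test no longer compares the arms, and for performance it brings the initial-simulation score back in.

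**Working it through.** **1. The plan's own figure.** Section 6.1 gives LS 71.90 (SD 18.59), SL 85.32 (SD 15.63), alpha 0.05, power 0.8 and N = 60. Two-sided testing and 1:1 allocation are assumed. Per arm, n = 2 × [18.59 × (1.960 + 0.842) / 13.42]² = 30.1, so 60 in total after rounding. This uses the LS SD. The pooled SD, √[(18.59² + 15.63²)/2] = 17.17, gives 26 per arm, or 52. The calculation is unadjusted, so the covariate problem does not alter N.

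**2. Which scores could serve as the covariate?**

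| Measure | LS | SL | Performance score? | Before the lecture in both arms? |
|---|---|---|---|---|
| Pre-intervention knowledge test | before lecture | before simulation and lecture | no | yes |
| Initial simulation (GRS, times) | after lecture | before lecture | yes | no |
| Knowledge test after the session | after both parts | after both parts | no | no |
| Final simulation | 3 months | 3 months | yes (the outcome) | no |

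No row is a performance score that precedes the lecture in both arms. Both simulations belong to the allocated sequence, so neither precedes randomization. The documents do not say whether the knowledge pre-test precedes randomization; they establish only that it precedes teaching.

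**3. Like with like.** With 60 students in teams of 3 to 4 there are 60/4 = 15 to 60/3 = 20 initial leaders, so 40 to 45 students do not lead at first. All lead in the final simulation.

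**4. Effect of using the initial-simulation score.** By the covariance identity, adjusted (SL-LS) = unadjusted (SL-LS) − b × (initial mean in SL − initial mean in LS), where b is the within-arm slope. If the lecture raises the LS initial score by L, the shift is +b × L, toward SL when both are positive. Let r be the correlation between a student's own initial and final performance, in SD units. For teams of 3, and with r = L = 0.5 assumed:
- Individual ratings: b = r, shift 0.5 × 0.5 = 0.25 SD.
- Error-free team mean: b = r, shift 0.25 SD.
- Team rating with 50% reliability: b = r/2, shift 0.125 SD.
- Leader's score given to the whole team: b = r/3, shift 0.083 SD.

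Simulation with 30 per arm and no true difference gave 0.251, 0.252, 0.126 and 0.084 SD. Over an assumed r of 0.3 to 0.7 and L of 0.25 to 0.78, the shift runs from 0.3 × 0.25 = 0.075 to 0.7 × 0.78 = 0.546 SD for individual ratings, and one third of that (0.025 to 0.182) for a shared leader score. With L = 0 there is none.

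**5. Power of the alternatives at 30 per arm.** The standardized effect is 13.42/17.17 = 0.78 with the pooled SD and 13.42/18.59 = 0.72 with the SD that reproduces N = 60. The correlation r between knowledge test and final GRS is assumed.

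| Analysis (d = 0.78) | r = 0.2 | r = 0.3 | r = 0.5 |
|---|---|---|---|
| ANCOVA on the knowledge test | 86% | 88% | 93% |
| Mixed model, random team intercept, no clustering | 80% | 80% | 89% |
| Same model, team ICC 0.1 (assumed) | 73% | 76% | 82% |

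Unadjusted power is about 84% at d = 0.78 and about 79% at d = 0.72. The mixed-model rows are simulated (1,500 runs, 17 df), with a standard error near √(0.8 × 0.2/1500) = 1 percentage point.

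**The case against.** The strongest reply is that section 6.2 says pre-randomization, and the initial simulation comes after allocation. Read literally, the plan excludes the score that would cause bias. That stands. A reader might infer that the trial will adjust for the initial simulation and so is biased toward SL; no section says so. What keeps the risk open is section 3.1, which uses the looser term baseline and words the performance and knowledge outcomes in parallel, as if each had its own earlier score.

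A reader might also infer a definite inflation of the false-positive rate. The documents give neither the slope nor the lecture effect. They also leave open whether the team session is rated per student or per team. The 0.78 at the top of the range in the working is the planning difference between sequences in an echocardiography study, not a lecture effect on a first simulation. No error rate can be claimed.

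Nor is it right that no performance is scored before teaching in either arm: SL's initial simulation precedes its lecture. That asymmetry between the arms is the source of the possible bias.

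The scope is also limited. The log-rank test and an unadjusted comparison of independent groups do not carry this bias, and the knowledge outcome has a proper baseline. Finally, choosing the knowledge test is partly preference, since leaving the GRS unadjusted is equally unbiased. None of these points supplies the missing covariate. The permission in 6.2 to adjust for imbalanced or prognostic baseline variables adds discretion without defining it.

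**Conclusion.** The plan is wrong as written on two counts. The covariate for the primary GRS model is not collected in the form described, so that model cannot be run as specified. The paired t-test does not suit two independent arms. Both conclusions follow from the schedule and need no assumption.

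The bias toward SL is conditional. It requires that the initial-simulation score be used, that the lecture improve it, and that it correlate positively with the final score within arms. Its size is unknown, from negligible to about half an SD over the assumed range. The case for correction rests on the undefined covariate and the wrong test, and both should be settled before any outcome data are examined.

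**What to change.** **Section 3.1.** Replace "This will be adjusted for baseline score" with: *The final GRS is adjusted for the pre-intervention knowledge-test score; initial-simulation GRS and times are not used as a covariate or paired value for the primary outcome.*

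**Section 6.2.** Replace the paired t-test with an independent two-sample (Welch) t-test. Replace the pre-randomization score with the pre-intervention knowledge-test score in both the GRS and the knowledge models. State that no Cox model uses initial-simulation performance. State which GRS analysis is primary and, if the mixed model is kept, what its random effect is. Dropping baseline adjustment of the GRS is an equally unbiased alternative.

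**Cost.** The change is wording only, with no new measurements and N still 60. The pre-test and the video scores must share a study ID. The knowledge test may predict the GRS only modestly, so the gain in power may be small. If a random intercept for initial-simulation team is fitted, power can fall below that of the unadjusted test, as the table in the working shows; that should be weighed when the primary analysis is named.

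### The leading test for the five time-to metrics in the primary outcome is an unadjusted log-rank test, which cannot deliver the baseline adjustment stated in section 3.1

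*Combined protocol and SAP*

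**What the plan says.** Section 3.1 (Outcome Measures) defines the primary outcome as the final global rating scale score "as well as the following “time-to” metrics; glucose check, IV access, chemistry panel order", followed by the times to the first-line and second-line drugs. That makes one score and five times. The closing sentence covers the whole list: "This will be adjusted for baseline score". It does not say which score is the baseline.

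Section 6.2 (Statistical Analysis) splits the methods. Scores are compared "with mixed effects linear models using pre-randomization score as a covariate", among other methods. Time-to-event measures are shown with Kaplan-Meier curves and medians and "tested with the log-rank test, and secondarily using Cox proportional hazards models". No strata or covariates are named for either. A general sentence follows: "Regression models may include adjustment for baseline variables imbalanced between arms or prognostic of outcome".

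Section 5.4 (Study Protocol) provides a knowledge test before teaching in both arms, ahead of the lecture in LS and ahead of the first simulation in SL (the sentence begins "The LS group will complete a pre-intervention knowledge test prior to the lecture and the SL group will complete a knowledge test prior to the"). For the secondary knowledge outcome, section 3.1 specifies a "15 Question MCQ test administered at the final assessment adjusted for the baseline score".

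**The concern.** Section 3.1 says that adjustment will happen. For the time-to metrics, section 6.2 leaves it to a secondary model whose covariates are optional. The leading p-value for five of the six primary measures therefore answers an unadjusted question, while the outcome definition states an adjusted one.

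Two things are at stake. First, with an adjusted and an unadjusted analysis both available and sections 3.1 and 6.2 pointing different ways, the choice of headline result is open to being made after the data are seen. Second, if students who start with more seizure knowledge act faster three months later, a test that ignores starting knowledge has less power to show an effect of teaching order. With about 60 students there is little to spare.

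**Working it through.** **1. The plan's own figure.** Section 6.1 gives means 71.90 and 85.32 (difference 13.42), SDs 18.59 (LS) and 15.63 (SL), alpha 0.05, power 0.8 and a sample size of 60. Taking alpha as two-sided (the plan does not state sidedness) and using the LS SD:

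n per arm = 2 × [18.59 × (1.960 + 0.842) / 13.42]² = 30.12

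This is 60 in total if rounded and 62 if rounded up, so 60 is reproduced. The calculation compares two means. It contains no event rate, hazard ratio or covariate, so it says nothing about power for the time-to metrics.

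**2. Can the leading test carry the adjustment?** A log-rank test without strata uses only arm, time and event status, so it cannot. The mixed model's baseline covariate is written for scores. The Cox model could carry one, but it is secondary and its covariates are optional.

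**3. Which baseline is available?** The first simulation cannot supply an individual pre-teaching performance score. Section 5.4 says "Both groups will complete the initial simulation in groups of 3-4 with one member acting as the leader", and in the LS arm it follows the lecture. The knowledge test is the only score that each student in both arms produces before teaching.

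**4. What might adjustment be worth?** The documents give no hazard ratio, event rate or link between score and times, so the following are assumptions:

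- 60 students, 30 per arm, treated as independent.
- Hazard = (ln 2 / control median) × exp(θ·arm + β·x), where x is the standardised baseline score and θ = ln 2.1.
- Censoring at 10 minutes, the length of the simulation.
- Control median of 3 or 6 minutes.

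The value 2.1 is close to the smallest effect that 60 events could detect with 80% power: exp[2 × (1.960 + 0.842) / √60] = 2.06.

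Power over 3,000 simulated trials per row, log-rank against Cox adjusted for x:

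| Hazard ratio per SD of score | Median 3 min (53–57 events) | Median 6 min (45–48 events) |
|---|---|---|
| 1.00 | 79% v 78% | 73% v 72% |
| 1.22 | 76% v 78% | 70% v 71% |
| 1.49 | 69% v 76% | 66% v 71% |
| 1.82 | 60% v 76% | 55% v 69% |
| 2.23 | 52% v 75% | 48% v 68% |

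The Monte Carlo standard error of each figure is at most √(0.5 × 0.5 / 3000) = 0.9 points. Further runs near 1.5 per SD gave gains of up to 8 points (70% v 78%). Further runs at 2.1 per SD gave 52% v 75% (median 3) and 50% v 68% (median 6), which are gains of 23 and 18 points. With no treatment effect, both tests rejected in about 5% to 6% of trials.

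**5. How strong are these associations?** For exponential times the variance of log time at a given score is π²/6 = 1.645, so the correlation is β / √(β² + 1.645). At 1.5 per SD, β = 0.405 and the correlation is 0.405 / √1.809 = 0.30. At 2.1 per SD, β = 0.742 and the correlation is 0.742 / √2.196 = 0.50.

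**The case against.** The strongest reply is that an unadjusted log-rank test followed by Cox models is a valid and conventional order in a randomised trial, and that only the wording of sections 3.1 and 6.2 is mismatched. Limiting the adjustment sentence in section 3.1 to the rating scale would remove the contradiction. Validity stands: the type I error is right. That edit would, however, leave any loss of power in place.

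Four stronger readings are tempting, and the documents do not support them.

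- A reader might infer that power is lost. It is lost only if the score predicts the times, and no document gives that association. If there is none, adjusting costs about 1 point.
- A reader might infer that the knowledge score goes unused. It is absent only from the log-rank test. It is the natural baseline for the secondary knowledge outcome, and it may enter the Cox model as a prognostic variable.
- A reader might infer that the baseline score in section 3.1 is the knowledge test. Section 3.1 does not say so, and in context it reads more naturally as a performance score. The difficulty is that no individual pre-teaching performance score exists.
- A reader might take a large gain as the expected one. Setting the log-rank test at about 80% power and assuming a correlation of 0.5 gives about 95% for adjusted Cox without censoring. That correlation is an assumption. A 15-question test taken before teaching need not predict times three months later that strongly.

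It also stands that smooth proportional-hazards times fit some metrics poorly. In both Appendix C scenarios, IV access fails at first and stage 2 opens after five minutes, so times to IV access and to a second-line drug are partly set by the script. Initial training in groups of 3–4 is not modelled either. The percentages compare the two tests and do not estimate the trial's power.

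**Conclusion.** The point holds as an inconsistency with a possible cost in efficiency, and it does not make the analysis invalid. That the leading test cannot deliver the adjustment in section 3.1 follows from the text alone and needs no assumed number.

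The size of the gain cannot be fixed from the documents. At 60 students, with a conditional treatment hazard ratio of 2.1 and 10-minute censoring, it runs from nothing (a cost of about 1 point), through 1 to 2 points at a hazard ratio of 1.22 per SD and 5 to 8 points at 1.5, to about 20 points at 2.1. The top of that range needs a strong association. The possible gain is much larger than the possible cost, the score is already collected, and the leading test should be settled before outcomes are seen, so the change is worth making.

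**What to change.** In section 3.1, name the pre-intervention knowledge test score as the baseline covariate for the time-to metrics.

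In section 6.2, make one pre-specified analysis the lead for each time-to metric: the between-arm test from a Cox model containing arm and that score as a continuous covariate. Keep Kaplan-Meier curves, medians and the unadjusted log-rank test as supportive. Do not add a conditional switch to a log-rank test stratified at the median score. It would leave the leading test open, and the split discards part of the information that the score carries.

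The cost is wording only, because the test is already taken and the Cox model is already planned. There are two downsides to state. The leading test will rely on proportional hazards given baseline knowledge, which is least certain for IV access and the second-line drug. The hazard ratio will be conditional on the score, so it should be reported as such.

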31. Kane S. Sample Size Calculator. ClinCalc.com. Published July 24, 2019. Accessed October 17, 2022. <https://clincalc.com/stats/samplesize.aspx>

**Appendix A:
Demographics:**

Please enter your age:

What is your experience with medical simulation?

a) No experience b) 1-5 simulation experiences c) 5-10 simulation experiences d) >10 simulation experiences

Before entering medicine please check any roles that apply?

- Background in ED Nursing
- Background as a paramedic or first responder?

Confidence Quiz:

Please rate your anxiety in the simulation experience from 1 to 5?

1 – Extremely anxious 5 – Not anxious at all

Please rate your confidence in managing pediatric seizures in the future?

1 – Not confident at all, 5 – extremely confident

Please rate your satisfaction with the educational experience (Simulation + Debrief + Lecture)?

1 – extremely dissatisfied , 5 extremely satisfied

Initial priorities

- Cardiorespiratory monitor, BP and temp
- Point of care glucose
- 100% oxygen via non-rebreather mask
- IV access
- Tylenol
- Primary survey
- Initial anti-seizure medication

Powered by **Dall E Everywhere**

Stabilization

Initial Management

- Initiate ABCs, cardiorespiratory and BP monitoring
- O₂ 10-15 L/min via non-rebreather mask
- Prioritize giving the first dose of benzodiazepine as early as possible, followed by checking blood glucose
- Monitor for respiratory depression, hypotension, arrhythmias
- Give acetaminophen 15 mg/kg/dose (MAX 650 mg) PR if febrile
- Consider other investigations:**
 - Electrolytes, blood gas, calcium, CBC, serum glucose
 - Other: anticonvulsant drug levels, LFTs, blood & urine culture

Primary Survey – A - Airway

Recognize	Assess for	Manage
A Airway Obstruction	
 Position (hyper/hypo extension) Patency (Blood, Vomiting) Need for protection 	
 Oral Suction Sniffing Position Oral Airway Jaw thrust Bag-mask ventilation

Primary Survey – B - Breathing

Recognize	Assess for	Manage
B Respiratory Failure	
 Apnea/poor effort Increased work of breathing Air entry Added Sounds: Wheeze/Crackles SpO₂, RR, End-tidal CO₂ 	
 Bag-mask ventilation Positive Pressure (HFNC, CPAP, BiPAP) Prepare for intubation if needed Medications for respiratory distress (Asthma) Pneumothorax – Needle decompression, Chest tube

Respiratory issues are typically secondary to airway compromise in seizures

Primary Survey – C - Circulation

Recognize	Assess for	Manage
C Shock	
 Tachycardia, Bradycardia Cap Refill (Fast/Slow) Pulses Hypotension (late sign) Hepatomegaly Check pelvis stability 	
 Think about access - IV, IO, Central Line Isotonic Fluid Bolus – 10-20ml/kg at a time Consider epinephrine or norepinephrine

Seizing patients should be tachycardic and normotensive or slightly hypertensive.
Hypotension and/or bradycardia is very concerning.

Primary Survey – D - Disability

Recognize	Assess for	Manage
D Severe Head Injury Raised ICP Seizure	
 GCS less than or equal to 8 Respond only to pain/unresponsive Cushing's Triad (Bradycardia, Hypertension, Irregular resp) 	
 Head of bed elevation, head midline Intubation/Sedation 3% hypertonic saline – 5ml/kg Hyperventilation if herniation (Blown Pupil) Neurosurgery consult

AVPU: Alert → Verbal → Pain → Unresponsive

Primary Survey – E - Exposure

E	Recognize	Assess for	Manage
	
 Rashes Signs of Trauma 	
 Purpura Bruising Abrasions 	
 Maintain Normothermia

Not always a core component of seizure assessment but may give clues to etiology

Estimating your patients weight

Practical Estimation based on Age:

- Infants <12mo: (age in months + 9)/2
- Children 1-5: (age + 5) x 2
- Children 5-14: Age x 4

When poll is active, respond at [pollev.com/[name]](https://poll.ev.com/[name])

You don't have an IV how can you give a benzodiazepine to stop the seizure?

IV access only	Oral
	Sublingual
	Intranasal
	Rectal
	Intraosseous
	Intramuscular

Powered by [Poll Everywhere](https://poll.ev.com)

First line Treatment

Phase 1 5-15 min

Prehospital	First Line Agents

 Give Midazolam IM/intranasal (NI see dosing table). Check blood glucose: If blood glucose <3.3 mmol/L (<60 mg/dL): Treat with D2BW 2 mL/kg/dose IV (MAX 100 mL/dose) OR D10W 5 mL/kg/dose IV (MAX 200 mL/dose). If still seizing after 5 minutes, give Midazolam second dose. MAX cumulative dose 10 mg in prehospital setting. 	No IV/IO Midazolam IM or IN: <13 kg: 0.2 mg/kg/dose; 13-40 kg: 5 mg/dose; >40 kg: 10 mg/dose; MAX 10 mg/dose
Emergency Department (ED) 
 Give benzodiazepine if two doses not already given prior to ED arrival (see dosing table). Check blood glucose if not already done. Treat hypoglycemia as above. Reassess blood glucose in 5 minutes. Give second benzodiazepine dose for ongoing seizures 5 minutes after first dose. When IV/IO access available, switch to IV/IO route. CAUTION: Do not give more than 2 doses of benzodiazepines.	IV/IO Lorazepam IV/IO: 0.1 mg/kg/dose; MAX 4 mg/dose Midazolam IV/IO: 0.1 mg/kg/dose; MAX 10 mg/dose

Reassess ABCs, monitor for respiratory depression. If still seizing give one of these second-line agents.

Respond at [pollev.com/[name]](https://poll.ev.com/[name])

6yr old patient who was seizing on the ward for 30 minutes and have received 3 doses of midazolam to try to abort their seizure. They now have very minimal respiratory effort. What is cause?

[figure not shown]
Prolonged Seizure
Poor positioning/Obstruction
To many benzodiazepines
Sepsis

Powered by [Poll Everywhere](https://poll.ev.com)

Benzodiazepines – First Line

Drug and route	Dose	Maximum
Midazolam	0.1 mg/kg	5 mg
• IV, IO		
• IM	0.2 mg/kg	10 mg
• Buccal	0.5 mg/kg	10 mg
• Intranasal	0.2 mg/kg	10 mg (5 mg per nostril)
Lorazepam	0.1 mg/kg	4 mg
• IV, IO, Buccal		
Diazepam	0.3 mg/kg	5 mg (<5 years); 10 mg (≥5 years)
• IV, IO		
• PR	0.5 mg/kg	20 mg

MAX DOSES: TWO

Side Effects of too many Benzodiazepines

- Respiratory depression
- Hypotension
- Sedation

Second Line Treatment

Repeat one different second line medication 5 mins after infusion

Phase 2
15-20 min

Drug	Dose	Age	Comments/Cautions
Levetiracetam	40 mg/kg/dose IV/IO (MAX 3000 mg/dose) infuse over 5 minutes	Any age	↓ side effects/drug interactions, low risk of psychosis
Fosphenytoin	20 mg phenytoin equivalent (PE)/kg/dose IV/IO (MAX 1000 mg PE/dose) infuse over 10 minutes	Any age	↓ BP, ↓ HR, arrhythmia; avoid in toxicologic seizures, choose alternate drug if phenytoin at home or consider partial loading dose of 10 mg PE/kg/dose In Canada, only available via Health Canada Special Access Program; caution in patients with liver dysfunction, mitochondrial disease, uremia disorder, thrombocytopenia or unexpected developmental delay
Valproic Acid	40 mg/kg/dose IV/IO (MAX 3000 mg/dose) infuse over 10 minutes	≥2 years	
Phenytoin	20 mg/kg/dose IV/IO (MAX 1000 mg/dose) infuse over 20 minutes	Any age	↓ BP, ↓ HR, arrhythmia; avoid in toxicologic seizures; choose alternate drug if phenytoin at home or consider partial loading dose of 10 mg/kg/dose; use only if Fosphenytoin not available
Phenobarbital	20 mg/kg/dose IV/IO (MAX 1000 mg/dose) infuse over 20 minutes	≥4 mos	Respiratory depression, especially in combination with benzodiazepines

Reassess ABCs, monitor for respiratory depression. If still seizing:

Equal Efficacy of all options
Levetiracetam can be given the fastest with the best side effect profile

[figure not shown]
When poll is active, respond at polllev.com/[name]

Which of these concentrations of dextrose can be given through a peripheral IV?

- D5 - 10ml/kg
- D10 - 5ml/kg
- D12.5 - 4ml/kg
- D25 - 2ml/kg
- D50 - 1ml/kg

Powered by [Poll Everywhere](https://polllev.com)

Hypoglycemia

[figure not shown]
When poll is active, respond at polllev.com/[name]

When does hyponatremia become concerning for causing seizures?

- < 135 mEq/L
- < 130 mEq/L
- < 125 mEq/L
- < 120 mEq/L
- < 115 mEq/L

Powered by [Poll Everywhere](https://polllev.com)

Hyponatremia

When poll is active, respond at polllev.com/[name]

Which of these patients does not need a CT scan?

- Post-Traumatic Seizure
- Status Epilepticus
- Febrile Seizure
- Focal Seizure
- None of the above

Powered by [Poll Everywhere](https://polllev.com)

Raised ICP/Trauma/Stroke

Necessary Investigations:

[figure not shown]
- Non-Contrast CT Scan

Band-Aids:

- Head of bed elevation
- Sedation
- Hypertonic saline
- Mannitol
- Hyperventilation

Managing secondary brain injury:

- Normothermia
- Normotension
- Normoglycemia

Definitive Management – NEUROSURGERY

Infection

Febrile Seizure:

- Between 6 months and 6 year with a temp >38.0C
- Absence of CNS infection/inflammation and no acute systemic abnormalities
- Seizures typically 5-10 mins with shorter post-ictal period of 5-10 mins.

Febrile Status Epilepticus

- Consider Meningitis/Encephalitis
- Blood Culture
- Urine Culture
- Consider LP/CSF if stable

Start antibiotics as soon as possible

Medications	
1	Ceftriaxone 750 mg/Intravenous for 10 days (3000 mg/Intravenous)
	ON
2	Ceftriaxone 100 mg/kg/Intravenous for 10 days (1000 mg/Intravenous)
	PLUS
3	Vancomycin 10 mg/kg/Intravenous for 10 days
	PLUS
4	Ampicillin 100 mg/kg/Intravenous for 10 days
	For patients < 2 months
	ON
5	Ampicillin 10 mg/kg/Intravenous for 10 days
	For patients < 6 months

If very sick: Don't delay antibiotics for cultures
Blood culture is still typically able to be obtained with IV

Disposition

Discharging:

- Ensure neurology follow up
- Outpatient EEG
- +/- Outpatient MRI

Brief Febrile Seizure – No further investigations needed

Admission Investigations:

- Neurology Consult
- MRI Brain
- Lumbar Puncture
- EEG
- Metabolic Workup

Children should be admitted to the hospital if they have prolonged seizures, refractory seizures or do not return to their baseline within 4-6 hours.

Resources

The flowchart outlines the management of pediatric status epilepticus, starting with initial assessment and stabilization, followed by first-line and second-line antiepileptic drug administration, and finally refractory status management with anesthetic agents.

References

- (2021) *Twitter*. Metrolina Trauma Advisory Committee. 30 August. Available at: <https://twitter.com/metrolina/trauma/status/1432333445758511588> (Accessed: January 12, 2023).
- Gary Hyding, O.D. (2019) *Dilated pupils: Causes and concerns*. *All About Vision*. Available at: <https://www.allaboutvision.com/conditions/dilated-pupils.htm> (Accessed: January 12, 2023).
- Lloyd, G. (2021) *Basic airway management*. *ACEM Learning*. Available at: <https://www.rcemlearning.co.uk/reference/basic-airway-management/#156839673154-RefBKG-1a10> (Accessed: January 11, 2023).
- *Newborn physical exam* (no date) *Stepwars*. Available at: https://www.stepwars.com/?page_id=4152 (Accessed: January 12, 2023).
- *Sindor - Lung Sounds - MEDZCOOL* (2018) *YouTube*. Available at: <https://www.youtube.com/watch?v=JdEK79i4dw> (Accessed: January 11, 2023).
- Chua W, Burns R, Stone K, Reid J. Pediatric Emergency Medicine Simulation Curriculum: Hyponatremic Seizures. *MedEPORTAL*. 12:10498. doi:10.15766/mep_2374-8265.10498
